1. REPORTING & ANALYSIS PLAN SYNOPSIS

Overview	Key Elements of the RAP
Purpose	
 This RAP details all of the planned analyses and output required for the final Clinical Study Report for study 201832.
Protocol	
 This RAP is based on the third amendment of the protocol (Dated: 25-May-2016) of study 201832 [GlaxoSmithKline Document Number 2015N231308_03].
Primary Objective	
 To evaluate the protective effect of fluticasone furoate/vilanterol (FF/VI) 100/25 mcg once-daily compared with fluticasone propionate (FP) 250 mcg twice-daily against exercise-induced bronchoconstriction in adolescent and adult subjects aged 12 to 50 with persistent asthma.
Primary Endpoint	
 Maximal percent decrease from pre-exercise FEV₁ following exercise challenge at 12 hours post evening dose at the end of the 2-week treatment period
Study Design	
 This is a multicenter, randomized, double-blind, double-dummy, crossover study with two 2-week treatment periods separated by a 2-week wash-out period. Subjects will participate in up to eight study visits (Visit 0 to Visit 7) over the course of the study and a follow up phone call approximately a week after Visit 7. Visits 1, 2, 3, 5 and 6 are evening visits that will be conducted between 5PM and 11PM. Visit 4 and Visit 7 are also evening visits that will begin between 5PM and 11PM and continue over a period of approximately 24 hours. Subjects will be required to attend three clinic visits during this 24-hour period.
Planned Analyses	
 No interim analysis is planned for this study. All planned analyses will be carried out once the clinical study database freeze (DBF) has taken place. Once this has been achieved, unblinding will occur and the analyses will be performed.
Primary Analysis Populations	
 The ITT Population will comprise all subjects randomized to treatment and who received at least one dose of trial medication. Randomized subjects will be assumed to have received trial medication unless definitive evidence to the contrary exists. This will constitute the primary population for all analyses of efficacy measures and safety measures. Outcomes will be reported according to the randomized treatment allocation. The PP Population will consist of all subjects in the ITT Population who do not have any full protocol deviations and have at least one treatment period without a partial deviation. Protocol deviations can either be full or partial. Subjects with only partial deviations in 1 treatment period will be considered part of the PP population but their data from the treatment period affected by the deviations will be excluded. The decision to exclude a subject, or part of their data, from the PP Population will be made prior to breaking the blind. This population will be used for confirmatory analyses of the primary efficacy endpoint only.

Overview	Key Elements of the RAP
Hypothesis	
Demonstration of efficacy will be based on a hypothesis testing approach, whereby the null hypothesis is that there is no difference between treatment groups for the endpoint of interest and the alternative hypothesis is that there is a difference between treatment groups
Primary Analyses	
The primary efficacy endpoint will be analysed using a mixed model repeated measures (MMRM) model allowing for fixed covariate effects of treatment, period baseline FEV₁, the mean of the two period baseline FEV₁ values, sex, age, treatment period and smoking history (number of pack years) as fixed effects, and a random intercept for each subject. The covariate-adjusted means for the primary endpoint for each treatment group will be presented together with the estimated difference between the treatment groups, a 95% confidence interval and a 2-sided p-value allowing the null hypothesis to be tested.

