4. ANALYSIS POPULATIONS

Population	Definition / Criteria	Analyses Evaluated
Total	
 This population will comprise all subjects screened and for whom a record exists on the study database 	
 The tabulations of reasons for withdrawal before randomization.
Intent-To-Treat (ITT)	
 This population will comprise all subjects randomized to treatment and who received at least one dose of study medication. Randomized subjects will be assumed to have received study medication unless definitive evidence to the contrary exists. Outcomes will be reported according to the randomized treatment allocation. 	
 Study population, efficacy and safety displays This will constitute the primary population for all analyses of efficacy measures and safety measures.
Per-Protocol (PP)	
 The PP Population will consist of all subjects in the ITT Population who do not have any full protocol deviations and have at least one treatment period without a partial deviation. Protocol deviations can be either full or partial. Subjects with only partial deviations in 1 treatment period will be considered part of the PP population but their data from the treatment period affected by the deviations will be excluded. Protocol deviations that would exclude subjects or part of their data from the PP population are defined in Appendix 1 (Definitions for Per-Protocol Population). 	
 This population will be used for confirmatory analysis of the primary efficacy endpoint only.
ITT (12-17 Years Old)	
 This will be a subset of the ITT population for subjects aged 12-17 years old. 	
 This population will be used for adolescent displays.
ITT (15 Years or Older)	
 This will be a subset of the ITT population for subjects aged 15 years or older. 	
 This population will be used for displays on the subset of subjects aged 15 years or older.

NOTES :

- Please refer to [Appendix 13: List of Data Displays](#), which details the population to be used for each display being generated.

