8. SAFETY ANALYSES

8.1. Safety Analyses

8.1.1. Overview of Planned Safety Analyses

The safety analyses will be based on the ITT population, unless otherwise specified.

[Table 5](#) provides an overview of the planned analyses, with further details of data displays being presented in [Appendix 13: List of Data Displays](#).

Table 5 Overview of Planned Safety Analyses

Display Type	Data Displays Generated		
	Table	Figure	Listing
Adverse Events			
Overview	Y		
AEs for Subjects not in ITT			Y ^[2]
Pre-Treatment AEs			Y
On-Treatment AEs	Y ^[3]		Y
Post-Treatment AEs	Y		Y
Most Frequent On-Treatment AEs (≥3% after rounding)	Y		
Top Ten Most Common On-Treatment AEs	Y		
Drug-Related AEs	Y		
Drug-Related SAEs	Y		
AEs Leading to Withdrawal	Y		Y
On-Treatment SAEs	Y		Y
Post-Treatment SAEs	Y		Y
Common On-Treatment Non-Serious AEs (≥3% without rounding including event numbers and drug-related event numbers)	Y		
On-Treatment SAEs (including event numbers and drug-related event numbers)	Y		
On-Treatment Fatal AEs (including event numbers and drug-related event numbers)	Y		
Post-Treatment Fatal SAEs (including event numbers and drug-related event numbers)	Y		
AEs of Special Interest	Y ^[1]		
SAEs of Special Interest	Y		
Relationship of AE System Organ Class, Preferred Term and Verbatim Text	Y		
Record of all Preferred Term's That Could Have Mapped to Special Interest Terms	Y		
Pneumonia			
On-Treatment Pneumonia	Y		Y
Post-Treatment Pneumonia	Y		Y
Chest X-ray			Y
Severe Asthma Exacerbations			
Severe Asthma Exacerbations	Y ^[3]		Y

Display Type	Data Displays Generated		
	Table	Figure	Listing
Other			
Vital Signs	Y		Y
Change from Baseline in Vital Signs	Y		
Family History of CV Risk Factors	Y		Y
IP Inhaler Malfunctions			Y

NOTES :

- Y = Yes display generated.
- [1]: Display will be based on the ITT population and repeated for the ITT (12-17 Years Old) population
- [2]: Display will be based on the inverse of the ITT population i.e. all subjects not in the ITT population
- [3]: Display will be based on the ITT population and repeated for the ITT (12-17 Years Old) population and also for the ITT (15 Years or Older) population

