10.1. Appendix 1: Definitions for Per Protocol Population

10.1.1. Protocol Deviations Impacting the Per Protocol Population

A protocol deviation which could affect all treatment periods will be considered a full deviation and will result in exclusion from the Per Protocol population. A protocol deviation which would only affect a specific treatment period will be considered a partial deviation and the data from the treatment period affected by the deviation will be excluded. If a subject has partial deviations in both treatment periods then the subject will be excluded from the Per Protocol population, however if a subject only has partial deviations in 1 treatment period, they will be considered part of the PP population but their data from the treatment period affected by the deviations will be excluded.

Reasons for protocol deviations that will impact the Per Protocol population include the following:

Number	Exclusion Description	Full or Partial?
1	Failure of inclusion criteria 3, 4, 5, 6 or 9; exclusion criteria 1, 3, 4, 7, 8, 9, 12, 13 or 15; randomization inclusion criteria 1 or 2 or randomization exclusion criteria 2, 4 or 5 as described in Section 6 of the protocol [GlaxoSmithKline Document Number 2015N231308_03].	Full
2	Remaining in the study after meeting the following withdrawal criteria described in Section 6 of the protocol [GlaxoSmithKline Document Number 2015N231308_03]: 
 Severe asthma exacerbation 	Full if during 1 st treatment period. Otherwise partial.
3	Taking of prohibited medication as described in Section 7.10.2 of the protocol [GlaxoSmithKline Document Number 2015N231308_03], where that medication could conceivably have an effect on a subject's efficacy.	Full if it affects both periods. Otherwise partial.
4	Overall treatment compliance for either DISKUS or ELLIPTA of < 80% or > 120%. (The protocol required subjects to take their study medication each day. For reporting and analysis purposes, treatment compliance of 80% and 120% are defined here as lower and upper limits for subjects to remain in the Per Protocol population.) Only treatment periods affected will be excluded.	Partial
5	Taking the wrong treatment at any time during the study. Only treatment periods affected will be excluded.	Partial

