10.4.1.2. Treatment States for Adverse Events and Severe Asthma Exacerbations

Treatment states for adverse events are described below. Severe asthma exacerbations will be treated in the same way, with the exacerbation start date used in place of the AE start date.

Treatment State	Definition
Pre-Treatment	AE start date \leq first dose date of the study -1
On-Treatment	First dose date of treatment period \leq AE start date \leq last dose date of treatment period + 1
Post-Treatment	AE start date \geq last dose date of study + 2 OR Last dose date of treatment period + 2 \leq AE start date \leq first dose date of next treatment period - 1

AEs occurring during the washout period or during the follow-up period are therefore classified as post-treatment and will be summarized under the treatment from the previous period.

Note: Time Since 1st Dose will be derived as follows:

- If the First Dose Date or the AE Onset Date are missing then => missing
- If First Dose Date > AE Onset Date then => AE Onset Date – First Dose Date
- If First Dose Date \leq AE Onset Date then => AE Onset Date - First Dose Date +1

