10.5. Appendix 5: Data Display Standards & Handling Conventions

10.5.1. Study Treatment & Sub-group Display Descriptors

Treatment Group Descriptions			
RandAll NG		Data Displays for Reporting	
Code	Description	Description	Order [1]
A	FF/VI 100/25mcg OD	FF/VI 100/25 OD	1
B	FP 250mcg BD	FP 250 BD	2

NOTES:

1. Order represents treatments being presented in TFL, as appropriate.

If a subject attends at least one scheduled clinic visit for a treatment period, then they will be counted as having taken part in that treatment period and will contribute to the population numbers (i.e. “Big N” numbers) for the treatment that they were randomized to receive in that period.

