10.5.3. Reporting Process & Standards

Reporting Process	
Software	

 The currently supported versions of SAS software will be used. 	
Reporting Area	
HARP Server	: uk1salx00175
HARP Area	: /arenv/arprod/gw685698_gw642444/mid201832/final/
QC Spreadsheet	: \\hlwdsntv006a\med_ds_rgm\Projects\Respiratory & Inflammation\Horizon\201832 (Exercise study)\Statistics\QC Tracking\
Analysis Datasets	

 Analysis and reporting (A&R) datasets will be created according to Integrated Data Standards Library (IDSL) standards. 	
Generation of RTF Files	

 RTF files will be generated. 	

Reporting Standards	
General	

 The current GSK Integrated Data Standards Library (IDSL) will be applied for reporting, unless otherwise stated: 
 4.03 to 4.23: General Principles 5.01 to 5.08: Principles Related to Data Listings 6.01 to 6.11: Principles Related to Summary Tables 7.01 to 7.13: Principles Related to Graphics 	
Formats	

 All data will be reported according to the treatment the subject was randomized to unless otherwise stated. Numeric data will be reported at the precision collected on the eCRF or recorded in the raw dataset if from non eCRF sources. For summaries and analyses the decimal places shown below will be applied in the data displays: 	

Reporting Standards		
Specification of Number of Decimal Places for Descriptive Statistics		
Label	Description	No. of decimal places (dp) more than raw data
N	Number of subjects in the treatment group	Always present to 0 dp
n	Number of subjects with non-missing values	Always present to 0 dp
Mean	Arithmetic Mean	1 dp
SD	Standard Deviation	2 dp
Median	Median	1 dp
Min.	Minimum	0 dp
Max.	Maximum	0 dp
Specification of Number of Decimal Places for Statistical Analysis		
Label	Description	No. of decimal places (dp) more than raw data
LS Mean	Adjusted mean for the treatment group	1 dp
LS Mean Change	Adjusted mean change from baseline for the treatment group	1 dp
Std Err	Standard error	2 dp
Difference	Treatment difference	1 dp
Odds Ratio	Treatment odds ratio	Always present to 2 dp
95% CI	95% Confidence interval around treatment difference/ratio	Same number of dp as the difference/ratio
p-value	p-value	Always present to 3 dp (or <0.001 or >0.999)
Planned and Actual Time		

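### Safety tables follow the randomised drug with no exception, so adverse events in any wrong-treatment period would be tabulated under a drug the subject did not take

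*SAP*

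**What the plan says.** One attribution rule covers efficacy and safety. Of the ITT population, SAP section 4 says: "This will constitute the primary population for all analyses of efficacy measures and safety measures". The SAP synopsis adds: "Outcomes will be reported according to the randomized treatment allocation". Protocol section 10.3.1 has the same rule. SAP section 10.5.3 makes it the general default: "All data will be reported according to the treatment the subject was randomized to unless otherwise stated".

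The safety section does not depart from it: "The safety analyses will be based on the ITT population, unless otherwise specified" (SAP 8.1.1). Denominators follow the same logic, because a subject who attends a visit in a period "will contribute to the population numbers (i.e. “Big N” numbers) for the treatment that they were randomized to receive in that period" (SAP 10.5.1). Adverse events starting in the washout or follow-up period "will be summarized under the treatment from the previous period" (SAP 10.4.1.2).

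The plan expects that wrong treatment may happen. SAP 10.1.1, item 5, names it as a partial deviation: "Taking the wrong treatment at any time during the study". SAP 4.1 and 10.1.1 exempt incorrect-treatment deviations from the rule that deviations are agreed before unblinding. Listing 6 sets randomised against actual treatments, and Listing 21 covers subjects given incorrect medication. The Per Protocol population does not reach the safety tables: "This population will be used for confirmatory analysis of the primary efficacy endpoint only" (SAP section 4).

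**The concern.** Analysis by randomised treatment protects an efficacy comparison from selection after randomisation. The safety displays here are descriptive, and none enters the testing hierarchy, so the rule protects no hypothesis test. In a wrong-treatment period it only puts events beside a drug to which the subject was not exposed.

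Adverse events are the only listed safety endpoint, and the comparison is between a LABA-containing combination and an inhaled steroid alone. The SAP also tabulates events of special interest to FF and/or VI by treatment. A serious or special-interest event on one drug could therefore be printed under the other. The plan already treats such a period as unfit for the Per Protocol efficacy analysis, yet lets it stand unaltered in the safety tables.

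**Working it through.** **Step 1. Is there an exception for safety anywhere?** The default in SAP 10.5.3 yields only where something else is stated. The places that could state it are:

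- SAP section 4: safety is on ITT, as randomised. There is no safety or as-treated population.
- SAP 8.1.1 and 8.2: ITT again. Nothing is said about treatment received.
- SAP 10.4.1.2: events are placed by the dose dates of the period, and later events follow the previous period's treatment. It does not say whether that means randomised or received, so the default applies.
- SAP 10.6.4: coding, special-interest terms and chest X-ray windows only.
- SAP 10.13.5: each safety table is on ITT or an age subset of it. None is an as-received repeat.

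No exception is found.

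**Step 2. What happens to one affected subject?** Suppose a subject is randomised to FF/VI in a period and takes FP instead. The period's on-treatment events go to the FF/VI column. Events in the following washout or follow-up go there too, through SAP 10.4.1.2. The subject also counts in the FF/VI denominator through SAP 10.5.1.

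**Step 3. Size of one error.** The plan's denominator reproduces from protocol section 10.2.1: 275 × 0.80 = 220 entering run-in; 220 × 0.30 = 66 randomised; 66 × 0.85 = 56.1, or 56 evaluable. Every subject is due both treatments, so a column holds up to 66 subjects.

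- One subject-period: 1/66 = 1.5%. With 56 subjects it is 1/56 = 1.8%.
- The common-event tables use a 3% threshold (SAP 8.1.1). 1/66 = 1.5% falls below it and 2/66 = 3.03% reaches it. One subject in the wrong column can therefore move a preferred term across the threshold.

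**Step 4. Effect on a difference in rates (all rates and error counts assumed).** Let m be the wrong periods per affected column and q = m/66. Errors in one column only give an observed difference of (pA − pB)(1 − q). The same number in both columns gives (pA − pB)(1 − 2q).

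| Assumed true rates | m | One column | Both columns |
|---|---|---|---|
| 20% v 10% (10 points) | 1 | 9.85 | 9.70 |
| 20% v 10% (10 points) | 5 | 9.24 | 8.48 |
| 10% v 5% (5 points) | 1 | 4.92 | 4.85 |
| 10% v 5% (5 points) | 5 | 4.62 | 4.24 |

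Aggregate dilution is small. What matters more is where a single rare event is printed.

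**Step 5. Why denominators must move too.** Assume 66 subjects attend both periods and the subject in Step 2 receives FP in both. By treatment received, FF/VI was taken by 65 subjects and FP by 66, counting that subject once. Moving the events but leaving SAP 10.5.1 unchanged would divide the FF/VI count by 66 when only 65 were exposed.

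**The case against.** The strongest case for leaving the plan alone is that nothing in it is inconsistent. The rule is stated the same way in the protocol and throughout the SAP, and no section promises as-received safety tables. Treatment packs are assigned through an interactive response system (protocol 7.2.2), and the documents give no dispensing-error rate, so there may be nothing to correct. If an error occurs, Listings 6 and 21, with the adverse event listings (11, 12, 14 and 15), let a reader find the subject and the event.

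Most of this stands. The rule is a prespecified convention, the effect is conditional, and no information is lost. What does not follow is that the tables are therefore right: a listing leaves the summary table and its percentages as they are.

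A reader might also infer that in a crossover one kit mix-up swaps both of a subject's periods. The documents do not support that. Study drug is dispensed separately at Visits 2 and 5 (protocol Table 3), and SAP 10.1.1 classes wrong treatment as partial, excluding only the affected periods. One wrong pack affects one period; swapping both would take two errors or an error at sequence level.

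**Conclusion.** The point holds as a minor improvement. As written, the plan would tabulate the events of a wrong-treatment period, and the later events assigned to it, under a drug not taken, and no planned display corrects this.

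The size is zero without an error. With one, about 1.5% of a column is affected, assuming 66 subjects in it. The dilution figures rest on assumed event rates and on 1 to 5 assumed errors, none of which comes from the documents. Efficacy, sample size and the testing hierarchy are untouched.

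The rule is worth settling in advance. Because wrong-treatment deviations need not be agreed before unblinding, a decision to re-tabulate safety would otherwise be made with the treatment codes known.

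**What to change.** Preferred change:

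- In SAP sections 4, 8 and 10.5.3, state that exposure, adverse event, exacerbation and vital-sign displays are by treatment actually received in each period. Keep efficacy by randomised treatment, and align the synopsis.
- In SAP 10.5.1, make the population numbers for safety displays follow treatment received, so that numerators and denominators match.
- In SAP 2.1, which now declares no departure from the protocol's planned analysis, record this departure from protocol section 10.3.1.
- Add a counting rule for a period with mixed exposure, for example attributing each event to the treatment most recently taken at onset.
- Count a subject who received the same drug in both periods once in that drug's column.

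Alternative: keep the as-randomised tables and prespecify an as-received repeat of the adverse event, serious adverse event and exacerbation tables, triggered by any wrong-treatment deviation. The counting rules would apply to the repeat.

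The cost is several linked SAP edits and a little programming. No new data are needed, because actual treatment is already captured for Listing 6. The drawback is that safety denominators may differ from efficacy denominators, which a table footnote can explain.

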2. SUMMARY OF KEY PROTOCOL INFORMATION

2.1. Changes to the Protocol Defined Statistical Analysis Plan

There were no changes or deviations to the planned statistical analysis specified in the third amendment of the protocol (Dated: 25-MAY-2016) of study 201832 [GlaxoSmithKline Document Number [2015N231308_03](#)].

2.2. Study Objective and Endpoints

2.2.1. Primary Objective

To evaluate the protective effect of fluticasone furoate/vilanterol (FF/VI) 100/25 mcg once-daily compared with fluticasone propionate (FP) 250 mcg twice-daily against exercise-induced bronchoconstriction in adolescent and adult subjects aged 12 to 50 with persistent asthma.

2.2.2. Primary Efficacy Endpoint

- Maximal percent decrease from pre-exercise FEV₁ following exercise challenge at 12 hours post evening dose at the end of the 2-week treatment period

2.2.3. Secondary Efficacy Endpoint

- Maximal percent decrease from pre-exercise FEV₁ following exercise challenge at 23 hours post evening dose at the end of the 2-week treatment period
- Proportion of subjects with a 30 minute post-challenge FEV₁ that was no more than 5% lower than their pre-exercise FEV₁ following the exercise challenge at 12 hours and 23 hours post evening dose at the end of the 2-week treatment period
- Weighted mean for percentage decrease from pre-exercise FEV₁ following exercise challenge at 12 hours and 23 hours post evening dose (weighted mean 0-60 min) at the end of the 2-week treatment period

